#### **7.1.1. Potential Cases of Acute Kidney Injury**

Participants exposed to IMP demonstrating transient or sustained increase in Screat (with decrease in Screat-based eGFR or eCrCl) require expedited evaluation to differentiate AKI from DICI. DICI is defined as transporter-mediated effect related to altered renal tubular creatinine handling without histological injury.

AKI may be due to one or more types of injury, including DIKI. Differentiation of DIKI from other causes of AKI and from DICI may require clinical, radiographic, histopathologic, and laboratory assessments, as well as nephrology consultation.

## Follow-up Assessments

The participant should return to the site for evaluation as soon as possible, preferably within 48 hours of awareness of the abnormal results.

Evaluation should include physical examination, laboratory tests, detailed medical and surgical history, review of all medications (including recreational drugs and supplements [herbal]), family history, sexual history, travel history, blood transfusion, and potential occupational exposure to chemicals.

Laboratory assessments should include simultaneous serum cystatin C (Scys) and serum creatinine (Screat) tests. Estimates of eGFR, eCrCl and Screat-based eGFR and combined Screat-Scys-based eGFR should also be derived using the appropriate equation described in [Appendix 7](#).

### Differentiating Acute Kidney Injury from DIKI

A confirmed Screat increase is defined as:

- (i)  $\geq 0.3 \text{ mg/dL} (\geq 26.5 \text{ } \mu\text{mol/L})$  within 48 hours OR
- (ii) confirmed Screat increase  $\geq 1.5$  times baseline (known or suspected to have occurred within the prior 7 days).

Based on the assessments performed, suspected AKI (including DIKI) may be differentiated from DIKI as follows.

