#### Adult participants

	AKI (including DIKI) Any one of the below	DIKI
Scys & Screat	Simultaneous, confirmed serum cystatin C (Scys) increase and confirmed Screat increase	Confirmed Screat increase without confirmed increase in reflex Scys AND Confirmed Screat-based eGFR decrease without confirmed combined Screat-Scys-based eGFR decrease.
eGFR	Decrease in Screat-based eGFR and combined Screat-Scys-based eGFR (when available)	
Albuminuria or proteinuria	Confirmed albuminuria increase (see Appendix 7 for Grades A1 to A3 quantitation)	
Urine volume	Urine volume $<0.5 \text{ mL/kg/h}$ for 6 consecutive hours	

Regardless of the presence or absence of increase in Scrat, DIKI and other causes of AKI may be suspected if either there is (i) new-onset or worsening albuminuria or proteinuria are detected.

All confirmed cases of clinically relevant decrease in kidney function should be considered potential cases of DIKI if no other reason for the kidney function abnormalities has been found.

If appropriate, nephrology consultation may be recommended to facilitate differentiation of renal parenchymal disease, pre-renal azotemia, and post-renal obstruction. All confirmed cases of clinically relevant decrease in kidney function should be considered potential cases of DIKI if no other reason for the kidney function abnormalities has been found.

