**Table 7. Protocol-Required Laboratory Assessments**

Hematology	Chemistry	Urinalysis	Other
Hemoglobin	Urea	Local Dipstick:	COVID-19 testing
Hematocrit	Creatinine	pH	Urine drug screening d
RBC count	Serum cystatin C a	Glucose (qual)	Pregnancy Test e
Platelet count	eGFR, eCrCl b	Protein (qual)	
WBC count	Glucose (fasting)	Blood (qual)	
Total neutrophils (Abs)	Calcium	Ketones	At Screening only:
Eosinophils (Abs)	Sodium	Nitrites	FSH f
Monocytes (Abs)	Potassium	Leukocyte esterase	HBsAg
Basophils (Abs)	Chloride		HBsAb
Lymphocytes (Abs)	Total CO 2 (bicarbonate)	Laboratory:	HCVAb
	AST, ALT	Microscopy and	HIV
MCV	Total bilirubin	Culture c	
MCH	Alkaline phosphatase		
MCHC	Uric acid		
	Albumin		
	Total protein		

- a. Scys: Screening or Baseline Scys is recommended to help differentiate post-baseline DIKI from DICI. Post-baseline, Scys is measured if and only if serum creatinine increase post-baseline is observed (see Section [7.1.1](#)).
- b. Screening and Baseline eGFR or eCrCl is measured with Screat-based formula. Age-specific kidney function calculation (see Section [10.7.2](#)) is recommended to assess presence or absence of post-baseline change in kidney function.
- c. Only if UTI is suspected and urine dipstick is positive for nitrites or leukocyte esterase or both.
- d. The minimum requirement for drug screening includes cocaine, THC, opiates/opioids, benzodiazepines, and amphetamines (others are site- and study- specific).
- e. Local urine testing will be standard for the protocol unless serum testing is required by local regulation or IRB/EC. See [SoA](#) for collection times.
- f. For confirmation of postmenopausal status only in females <60 years old and not using hormonal or HRT only.

The investigator must review the laboratory report, document this review, and record any clinically relevant changes occurring during the study in the AE section of the CRF.

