## 10.7. Appendix 7: Kidney Safety: Monitoring Guidelines

### 10.7.1. Laboratory Assessment of Change in Kidney Function and Detection of Kidney Injury

Standard kidney safety monitoring requires assessment of baseline and postbaseline Screat measurement to estimate kidney function [Screat-based eGFR] or creatinine clearance [eCrCl]. Obtaining Screening or Baseline Scys and postbaseline reflex Scys (if confirmed Screat increase  $\geq 0.3$  mg/dL) makes it feasible to distinguish AKI from DICI. If Screat increase is confirmed after baseline, then reflex measurement of Scys is indicated:

**ADULTS:** Currently, 2021 CKD-EPI eGFR equations (Screat only-based and combined Screat plus Scys-based) are valid for use in adults only. At baseline Screat and Scys values are needed to calculate 2021 CKD-EPI eGFR by Screat only-based equation (see Table 10.7.2.1.) and by combined Screat plus Scys-based equation. When post-baseline Screat increase  $\geq 0.3$  mg/dL is confirmed, then reflex Scys measurement is needed to enable post-baseline comparison of eGFR changes (Screat only-based eGFR and combined Screat plus Scys eGFR).

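### Does the kidney-injury table in Protocol Section 7.1.1 need changing because it contrasts AKI (including DIKI) with DIKI?

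*Protocol*

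**What the plan says.** Section 7.1.1 opens by stating that participants with a creatinine rise "require expedited evaluation to differentiate AKI from DICI". It defines DICI as an effect on creatinine handling without histological injury. It then says that "AKI may be due to one or more types of injury, including DIKI", and that "Differentiation of DIKI from other causes of AKI and from DICI" may need several kinds of work-up.

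The sub-section on differentiation defines a confirmed creatinine rise and leads into the adult table with "suspected AKI (including DIKI) may be differentiated from DIKI as follows". The left column is headed AKI (including DIKI). The right column is headed DIKI, and its criteria begin "Confirmed Screat increase without confirmed increase in reflex Scys"; they also require a fall in creatinine-based eGFR without a fall in the combined creatinine and cystatin C eGFR. The text under the table adds that, whether or not creatinine rises, "DIKI and other causes of AKI may be suspected" if albuminuria or proteinuria is new or worse.

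Two other places describe what cystatin C is for. Table 7 footnote a recommends a screening or baseline value "to help differentiate post-baseline DIKI from DICI". Section 10.7.1 says that having baseline and reflex values "makes it feasible to distinguish AKI from DICI".

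**The concern.** A category cannot be told apart from one of its own members, yet the lead-in and the column headers ask for that. The right-hand criteria describe creatinine rising alone, the pattern that the rest of the protocol places on the DICI side. DICI is not mentioned in the sub-section or its table, so the category named in the section's stated purpose has no labelled criteria in the only table that gives any.

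What could be at stake is the name of an adverse event. Section 10.3.3 asks that, where possible, the diagnosis rather than its signs be recorded. An investigator who took the header at face value could record an isolated creatinine rise as drug-induced kidney injury, a term that implies both injury and drug causation. Treatment-emergent adverse events are a secondary endpoint, and with about 12 participants one affected participant would be 1/12 = 8.3% of the study. The documents give no expected rate of isolated creatinine rises, so this is the size of one case and not a forecast.

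**Working it through.** The plan gives no figure to reproduce. The check sets the passages side by side and then asks what depends on the label.

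**1. Which contrast does each place draw?**

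| Place | Contrast | DIKI uses | DICI uses |
|---|---|---|---|
| Section 7.1.1, opening | AKI against DICI; DIKI against other AKI and against DICI | 2 | 3 |
| Section 7.1.1, sub-heading and lead-in | AKI against DIKI; AKI (including DIKI) against DIKI | 3 | 0 |
| Section 7.1.1, adult table and text below it | AKI (including DIKI) against DIKI | 5 | 0 |
| Table 7, footnote a | DIKI against DICI | 1 | 1 |
| Section 10.7.1 | AKI against DICI | 0 | 1 |
| Appendix 10, abbreviations | the two terms defined separately | 1 | 1 |

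The disputed stretch has 3 + 5 = 8 uses of DIKI and none of DICI. DICI appears 3 + 1 + 1 + 1 = 6 times elsewhere.

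**2. How many of the 8 uses conflict?** Two: the second DIKI in the lead-in, and the right-hand header. The sub-heading is ambiguous, because the opening also speaks of separating DIKI from other causes of AKI. The other five (the DIKI in each of the two *including* phrases, and three in the text below the table) treat DIKI as an injury, as the rest of the protocol does. 2 + 1 + 5 = 8.

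**3. Can a reader recover the meaning?** Yes, within the section. The opening states the comparison, defines DICI and makes DIKI a type of AKI. The left-hand header already includes DIKI, so the right-hand one cannot be taken literally without contradicting its neighbour.

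**4. What uses the label?**

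- Discontinuation of study intervention (Section 7.1): the listed reasons are an adverse event that in the investigator's view requires it, pregnancy, and a positive COVID-19 test. None is defined by AKI, DIKI or DICI.
- Kidney grading (Section 10.7.3): based on eGFR bands and the albumin-to-creatinine ratio.
- Laboratory summaries (SAP Sections 3.5.2 and 6.5.2): based on sponsor reporting standards.
- Planned analyses (SAP Appendix 1): no row refers to these categories.
- Primary endpoints: plasma Cmax and AUC, which the label does not touch.

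The one route left is the wording of an individual adverse-event record.

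**The case for a change.** The best case for acting is that this is the protocol's only table of classification criteria for the distinction, that the conflicting contrast occurs in more than one place, and that correcting it would be cheap. A simple misreading of the PDF is also not the obvious explanation: the text has DICI correctly in four other places, and the paragraphs under the table contain a repeated sentence and a list with an item (i) but no (ii), which look like editing faults. All of that is fair, and the literal inconsistency stands.

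What does not stand is the consequence. For an event to be misnamed, an investigator would have to pass over the section's opening and the adjacent header and take a diagnosis from a column label. Section 10.3.3 has the diagnosis drawn from signs, symptoms and other clinical information. Section 7.1.1 says the distinction may need imaging, histopathology and nephrology input, offers the table only as a way the categories *may* be separated, and treats a confirmed decrease in kidney function as potential DIKI only when no other cause is found.

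The origin of the slip is also unsettled. The terms differ by one letter, the places in doubt lie close together, and single characters are unreliable elsewhere in the extracted text. Serum creatinine is abbreviated Scrat once under this table, and the hepatitis C antibody abbreviation in exclusion criterion 10 loses its last letter between the synopsis and Section 5.2.

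**Conclusion.** The observation is accurate but clerical. In the text as read, two labels, and arguably a sub-heading, conflict with the opening of the same section, Table 7 footnote a and Section 10.7.1. Correcting them would alter no laboratory criterion, procedure, data item, analysis set, planned summary or conclusion of the trial, so no change to the plan is called for.

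This rests on two things. The printed criteria are taken as they stand, and no view is offered on them or on clinical management. Investigators are assumed to read the table together with the paragraph that opens its section. Whether the signed protocol page carries the same letters cannot be settled from the extracted text, but the conclusion is the same either way: if it does, the wording can be reconciled as ordinary editorial tidying; if it does not, there is nothing to correct.

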#### Adult participants

	AKI (including DIKI) Any one of the below	DIKI
Scys & Screat	Simultaneous, confirmed serum cystatin C (Scys) increase and confirmed Screat increase	Confirmed Screat increase without confirmed increase in reflex Scys AND Confirmed Screat-based eGFR decrease without confirmed combined Screat-Scys-based eGFR decrease.
eGFR	Decrease in Screat-based eGFR and combined Screat-Scys-based eGFR (when available)	
Albuminuria or proteinuria	Confirmed albuminuria increase (see Appendix 7 for Grades A1 to A3 quantitation)	
Urine volume	Urine volume $<0.5 \text{ mL/kg/h}$ for 6 consecutive hours	

Regardless of the presence or absence of increase in Scrat, DIKI and other causes of AKI may be suspected if either there is (i) new-onset or worsening albuminuria or proteinuria are detected.

All confirmed cases of clinically relevant decrease in kidney function should be considered potential cases of DIKI if no other reason for the kidney function abnormalities has been found.

If appropriate, nephrology consultation may be recommended to facilitate differentiation of renal parenchymal disease, pre-renal azotemia, and post-renal obstruction. All confirmed cases of clinically relevant decrease in kidney function should be considered potential cases of DIKI if no other reason for the kidney function abnormalities has been found.

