### 10.7.2. Age-Specific Kidney Function Calculation Recommendations

#### 10.7.2.1. Adults (18 Years and Above)—2021 CKD-EPI Equations

eGFR (mL/min/1.73 m^2)

2021 CKD-EPI Screat Only	Screat (mg/dL)	Scys (mg/L)	Recommended eGFR Equation
Female	if $\leq 0.7$	NA	$eGFR = 143 \times (Screat/0.7)^{-0.241} \times (0.9938)^{Age}$
Female	if $> 0.7$	NA	$eGFR = 143 \times (Screat/0.7)^{-1.200} \times (0.9938)^{Age}$
Male	if $\leq 0.9$	NA	$eGFR = 142 \times (Screat/0.9)^{-0.302} \times (0.9938)^{Age}$
Male	if $> 0.9$	NA	$eGFR = 142 \times (Screat/0.9)^{-1.200} \times (0.9938)^{Age}$
2021 CKD-EPI Screat-Scys Combined	Screat (mg/dL)	Scys (mg/L)	Recommended eGFR Equation
Female	if $\leq 0.7$	if $\leq 0.8$	$eGFR = 130 \times (Screat/0.7)^{-0.219} \times (Scys/0.8)^{-0.323} \times (0.9961)^{Age}$
Female	if $\leq 0.7$	if $> 0.8$	$eGFR = 130 \times (Screat/0.7)^{-0.219} \times (Scys/0.8)^{-0.778} \times (0.9961)^{Age}$
Female	if $> 0.7$	if $\leq 0.8$	$eGFR = 130 \times (Screat/0.7)^{-0.544} \times (Scys/0.8)^{-0.323} \times (0.9961)^{Age}$
Female	if $> 0.7$	if $> 0.8$	$eGFR = 130 \times (Screat/0.7)^{-0.544} \times (Scys/0.8)^{-0.778} \times (0.9961)^{Age}$
Male	if $\leq 0.9$	if $\leq 0.8$	$eGFR = 135 \times (Screat/0.9)^{-0.144} \times (Scys/0.8)^{-0.323} \times (0.9961)^{Age}$
Male	if $\leq 0.9$	if $> 0.8$	$eGFR = 135 \times (Screat/0.9)^{-0.144} \times (Scys/0.8)^{-0.778} \times (0.9961)^{Age}$
Male	if $> 0.9$	if $\leq 0.8$	$eGFR = 135 \times (Screat/0.9)^{-0.544} \times (Scys/0.8)^{-0.323} \times (0.9961)^{Age}$
Male	if $> 0.9$	if $> 0.8$	$eGFR = 135 \times (Screat/0.9)^{-0.544} \times (Scys/0.8)^{-0.778} \times (0.9961)^{Age}$

Inker LA et al. N Engl J Med. 2021;385:1737-49.

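### The Section 7.1.1 kidney table conflicts with the protocol's own combined eGFR equation: read literally, a creatinine-only rise meets the acute kidney injury column

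*Protocol*

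**What the plan says.** Protocol Section 7.1.1 says that participants with a creatinine rise "require expedited evaluation to differentiate AKI from DICI". It gives the benign alternative a definition: "DICI is defined as transporter-mediated effect related to altered renal tubular creatinine handling without histological injury". Section 10.7.1 adds that baseline cystatin C (Scys) together with a reflex Scys "makes it feasible to distinguish AKI from DICI".

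The table for adult participants has two columns.

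- The first is headed "AKI (including DIKI) Any one of the below". Its rows cover Scys with serum creatinine (Screat), eGFR, albuminuria or proteinuria, and urine volume. The eGFR row is "Decrease in Screat-based eGFR and combined Screat-Scys-based eGFR (when available". Unlike the Scys and albuminuria rows, it does not ask for confirmation. It sets no minimum change.
- The second column is the creatinine-only one. It requires "Confirmed Screat increase without confirmed increase in reflex Scys AND Confirmed Screat-based eGFR decrease without confirmed combined Screat-Scys-based eGFR decrease". It is headed DIKI, as is the subsection above it, although the definition in 7.1.1, footnote a of Table 7 and Section 10.7.1 all show that DICI is the intended contrast.

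A confirmed Screat increase is defined as at least 0.3 mg/dL within 48 hours, or at least 1.5 times baseline. No section defines a decrease, or a confirmed decrease, in eGFR. The follow-up text sends the reader to Appendix 7 for the equations, where the relevant block is headed "2021 CKD-EPI Screat-Scys Combined".

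**The concern.** The table uses a fall in combined eGFR to separate injury from a change in creatinine handling. Combined eGFR is itself computed from creatinine. If it must fall whenever creatinine rises and cystatin C stays put, it cannot do that job, and it pulls against the Scys condition, which can. Because one row is enough for AKI, the eGFR row overrides the Scys evidence.

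At stake is the description of a safety finding. TEAEs and laboratory abnormalities with and without itraconazole are a secondary endpoint, and Section 4.2 expects higher PF-07817883 exposure with itraconazole. In a study of about 12 people, a single creatinine-only case labelled as possible kidney injury would stand out.

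**Working it through.** The plan states no figure on this point, so there is nothing to reproduce. The check applies the Section 10.7.2.1 equations to the 7.1.1 thresholds.

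**Inputs from the protocol.** Combined eGFR = c × (Screat/κ)^a × (Scys/0.8)^b × 0.9961^Age.

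- Women: c = 130, κ = 0.7; a = −0.219 up to κ, −0.544 above.
- Men: c = 135, κ = 0.9; a = −0.144 up to κ, −0.544 above.
- Both sexes: b = −0.323 up to Scys 0.8 mg/L, −0.778 above.
- Eligibility: age 18 to 65, eGFR at least 75.

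**Assumed.** Baseline Screat from 0.4 mg/dL upwards and Scys 0.5 to 1.2 mg/L. DICI is modelled as Screat up with Scys unchanged.

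**Step 1: direction.** Every creatinine exponent is negative, and the curve is continuous at κ because the ratio there is 1. With Scys fixed, combined eGFR therefore falls at every rise in Screat. A grid over both sexes, ages 18 to 65, Screat 0.4 to 3.0 and Scys 0.5 to 1.3 gave no exception in 422,688 steps.

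**Step 2: size.** With Scys and age fixed, the ratio of combined eGFR depends on Screat alone.

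- Smallest fall, a man going from 0.6 to 0.9 mg/dL (both +0.3 and ×1.5, all at or below κ): 1 − 1.5^(−0.144) = 5.7%.
- Largest fall, ×1.5 entirely above κ: 1 − 1.5^(−0.544) = 19.8%.

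| Screat rise | Women | Men |
|---|---|---|
| +0.3 mg/dL | 11.5–17.6% | 5.7–14.5% |
| ×1.5 | 8.5–19.8% | 5.7–19.8% |

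**Step 3: two worked records, age 40, Scys 0.8 throughout.**

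- Man, Screat 0.9 to 1.2. Screat-based eGFR: 110.7 × (4/3)^(−1.2) = 78.4. Combined eGFR: 115.5 × (4/3)^(−0.544) = 98.7, a fall of 14.5%.
- Woman, Screat 0.7 to 1.0. Screat-based eGFR: 111.5 × (1/0.7)^(−1.2) = 72.7. Combined eGFR: 111.2 × (1/0.7)^(−0.544) = 91.6, a fall of 17.6%.

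In both, each eGFR has decreased, so the AKI eGFR row is met. Scys has not risen, so the first condition of the creatinine-only column is met. Its second condition fails if any confirmed fall counts as a decrease.

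**Step 4: what would offset the fall.** Where Scys stays in one segment, the fall in Scys needed is 1 − (ratio from step 2)^(1/|b|).

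- Smallest: 1 − 1.5^(−0.144/0.778) = 7.2%.
- Largest: 1 − 1.5^(−0.544/0.323) = 49.5%.
- The man in step 3: 1 − (4/3)^(−0.544/0.323) = 38.4%.

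**Step 5: measurement noise.** Take the least favourable kind of record: a man aged 30, Screat 0.6 to 0.9, Scys 0.95 with no true change. Assume within-person CVs of 3%, 5% and 8% on both markers, and keep simulated records with a rise of at least 0.3 mg/dL on both post-baseline samples. Combined eGFR then falls on both samples in 97%, 86% and 75% of records. From 0.7 to 1.0 mg/dL the figures are 99.8%, 95% and 85%.

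**The case against.** The strongest reply is that the table is not an algorithm. The sentence introducing it is permissive. Section 7.1.1 says that the distinction may need clinical, imaging, histological and laboratory assessment and a nephrology opinion. Potential DIKI is reserved for confirmed, clinically relevant declines with no other explanation. This stands, and it limits the consequence.

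A second reply is that the creatinine-only column speaks of a confirmed combined eGFR decrease, so an implied size threshold could let a participant in. That is possible, but no threshold is stated. The AKI row has neither a threshold nor a confirmation requirement, so the participant would then meet both columns.

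A third is that the Scys condition already separates the cases. It does, but one row is enough for AKI, so it does not prevail.

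Three stronger readings are tempting, and the documents do not support them.

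- A reader might infer that the creatinine-only column can never be reached. Step 4 shows that a Scys fall as small as about 7% can offset the rise, which is within plausible noise, and step 5 shows the result is usual but not universal.
- A reader might infer that random variation would trigger the eGFR row at routine samples. Footnote a of Table 7 restricts post-baseline Scys to cases where creatinine has risen, so combined eGFR is not available at each routine sample.
- A reader might infer that the study's analyses are affected. The SAP assesses laboratory data against sponsor reporting standards, and Section 10.7.3 grades kidney-function decline by KDIGO eGFR bands. No endpoint, analysis set or summary uses the AKI/DICI split.

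**Conclusion.** The conflict is real and minor. With Scys unchanged, a creatinine rise at the Section 7.1.1 thresholds lowers combined eGFR by about 6% to 20% in eligible participants. Read literally, it meets the AKI eGFR row and fails the second condition of the creatinine-only column. The direction follows from the sign of the exponents. The range rests on the assumed baseline values, and the conclusion on Scys not falling by the roughly 7% to 50% needed to offset the rise. The effect the protocol defines as DICI would therefore usually be classed as AKI.

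If baseline Scys is missing (Table 7 only recommends it), the qualifier on availability appears to leave the fall in Screat-based eGFR alone, which a creatinine-only rise also meets. Correcting the DIKI heading does not remove the conflict.

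The consequence is confined to how a creatinine-only effect is classified in safety evaluation and reporting. The primary PK analysis is untouched.

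**What to change.** Reconcile the differentiation text and adult table in Section 7.1.1 with the DICI definition in the same section, with Section 10.7.1 and with the Section 10.7.2.1 equations. The revised table should:

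- make the two columns mutually exclusive;
- not let a creatinine-only rise with unchanged Scys satisfy the AKI eGFR row by itself;
- state what change in combined eGFR counts as a (confirmed) decrease, and apply it identically in both columns;
- correct the DIKI/DICI labels.

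The criterion and any threshold are for the sponsor's medical lead. One arithmetical fact bears on that choice: the fall grows with the creatinine rise. A doubling above κ with Scys unchanged gives 1 − 2^(−0.544) = 31.4%, so a size threshold alone moves the conflict to larger rises and does not remove it.

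The cost is a wording change to one table and its label. The downside is small: the AKI eGFR row becomes less inclusive for isolated creatinine rises, while the Scys, albuminuria/proteinuria and urine-volume rows remain.
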